5.15 Method of Assigning Patients to Treatment Groups

For each dose cohort, two sentinel patients who meet all screening and eligibility criteria will be assigned randomly in a 1:1 ratio on Day 1 to receive either bempegaldesleukin/SOC or placebo/SOC. Following CRC review of the blinded safety and tolerability data from the first 72 hours after study drug administration for the 2 sentinel patients, the CRC will determine whether additional patients who meet all screening and eligibility criteria will be randomized in a 1:1 ratio within the dose group. Study drug administration will be staggered by 72 hours for every 2 patients (1 bempegaldesleukin/SOC and 1 placebo/SOC) to allow for Medical Monitor review of the blinded safety and tolerability data before the next 2 patients are randomized. As stated in Section 5.3.1, patients who drop out of the study for reasons other than a DLT, before the DLT evaluation period (Days 1 to 7) has elapsed, may be replaced. Therefore, in each dose cohort, a maximum of 10 patients will complete the 7-day DLT evaluation period (ie, a total of 5 patients who receive bempegaldesleukin/SOC and 5 patients who receive placebo/SOC). Study

drug assignment will occur in a blinded fashion in accordance with a computer-generated randomization scheme prepared by Nektar or its designee.

Each patient will be assigned a unique patient number after signing the ICF. Patient numbers will be used on all patients' study information. Patient numbers will not be reassigned.

[figure not shown]
An Interactive Response Technology (IRT) will be employed to manage patient randomization.

Nektar will supply bempegaldesleukin from a central source. Choice of standard of care for an individual patient will depend on what drug products are available at each medical center and the Investigator's choice.

6.0 INVESTIGATIONAL PRODUCT(S)/STUDY DRUGS

Table 12 provides the study treatments that will be administered in this study.

[figure not shown]
Table 12:Study Treatments Administered

6.1 Bempegaldesleukin (NKTR-214)

Bempegaldesleukin is the International Nonproprietary Name (INN) for NKTR-214.

6.1.1 Drug Description and Formulation

6.1.2 Drug Packaging and Labeling

Nektar Therapeutics Confidential and Proprietary Each vial will be labeled with the study drug number/name, strength, name of the Sponsor, storage condition, lot number, and the required cautionary statement.

6.1.3 Drug Reconstitution and Handling

Refer to the Pharmacy Manual for detailed drug handling and administration information.

6.1.4 Drug Storage

6.1.5 Drug Shipment

Refer to the Pharmacy Manual for

additional details for ordering drug supply.

6.2 Placebo: Preparation, Storage, and Packaging

An unblinded pharmacist will prepare the placebo for infusion according to the instructions in the Pharmacy Manual.

The placebo dosing solution will be obtained as commercially available 0.9% Sodium Chloride Solution for Injection (USP).

6.3 Standard of Care: Preparation, Storage, and Packaging

Refer to the appropriate labeling requirements for details.

6.4 Study Drug Accountability and Reconciliation

Bempegaldesleukin will be supplied to the Investigator by Nektar Therapeutics or its designee. Depending on local health authority guidelines and drug availability, the standard of care may be obtained through commercial supply, the site pharmacy, or through a central depository. Depending on source of supply per specific country requirements, the packaging and labeling may vary. Products will be labeled to meet local country requirements. Please refer to the Pharmacy Manual for detailed information. Study drug supplies must be kept in an appropriate, secure, locked area and stored in accordance with the conditions specified on the labels. Depending on local health authority guidelines, IV fluids and associated supplies (IV administration sets, calibrated pumps) may be obtained through commercial supply, the site pharmacy, or through a central depository.

The Investigator, pharmacist, or designee must maintain an accurate record of dispensing the study drug in a Drug Accountability Log, a copy of which must be given to Nektar Therapeutics.

The Drug Accountability Log may record specifics to study drug dispensation such as:

- Records of product delivery, inventory, temperature monitoring, destruction, and return as per Sponsor's instructions.
- Doses prepared, time prepared, doses dispensed.
- Doses and/or vials destroyed.

The Drug Accountability Log will be reviewed by the monitor during site visits and at the completion of the study.

7.0 ASSESSMENT OF SAFETY

7.1 AE Definition and Assessment

An AE is defined as any untoward medical occurrence in a clinical investigation patient administered a pharmaceutical product, at any dose, not necessarily related to the treatment.

An AE can therefore be any unfavorable and unintended sign, symptom, or disease temporally associated with the use of a medicinal product, whether or not considered related to the medicinal product. An AE can also arise from any use of the drug and from any route of administration, formulation, dose, or overdose. This definition includes intercurrent illnesses or injuries, and exacerbation of preexisting conditions. Clinical laboratory, vital sign, or physical examination abnormalities will only be reported as AEs if they are deemed clinically significant by the Investigator (eg, associated with signs and symptoms, require treatment, or require follow-up).

An AE does not include:

- Pre-existing diseases or conditions present or detected before start of study drug(s) administration that do not worsen or increase in severity or frequency after the administration of study drug(s).
- Overdose of either study drug(s) or concomitant medication without any signs or symptoms.

7.2 Monitoring AEs

All AEs will be assessed by the Investigator and recorded, including but not limited to, the following: the event term, the date of onset and resolution, seriousness, severity, relationship to study drug(s), outcome, treatment of the event, and action taken with the study drug(s). AEs will be reported starting immediately after the patient has been administered the first dose of study drug(s) until 30 days following the last dose of study drug(s).

An event occurring after the patient has provided informed consent, but before the first dose of study treatment, will be collected as medical history unless the event is either new and attributed to protocol-mandated procedures by the Investigator or there is a significant change in the rate of occurrence or an increase in the severity of the pre-existing condition which is judged to be clinically important and attributed to the protocol-mandated procedures by the Investigator. Under the latter 2 circumstances, the event will be considered an AE and will be captured as such.

• Example 1: Thrombophlebitis associated with a blood draw for assessments required prior to dosing per protocol is an event that is related to protocol-mandated procedures. In this scenario, the event of "thrombophlebitis" will be captured as an AE, and it will be documented as being "unrelated" to study drug(s), as applicable.

• Example 2: An ankle sprain following an unexpected fall from a flight of stairs while at home, after the patient has provided informed consent, but before the first dose of study drug(s), is clearly unrelated to any protocol-mandated procedures and would therefore be captured as medical history.

7.3 Grading of AEs

The severity of an event and the seriousness are not to be considered synonymous. The severity is grading the intensity of an event. The seriousness of event is based on the patient/event outcome or action criteria. All AEs, except for cytokine release syndrome, will be assessed for severity using the National Cancer Institute (NCI) Common Terminology Criteria for Adverse Events (CTCAE) version 5.0 guidelines. For cytokine release syndrome, the modified CTCAE CRS grading scale should be used to assess severity (see Appendix 3). If a particular AE is not listed in the NCI CTCAE, the following criteria will be used:

- Grade 1 = Mild (event results in mild or transient discomfort, not requiring or needing only minimal intervention or treatment; does not limit or interfere with daily activities [eg, insomnia, mild headache]).
- Grade 2 = Moderate (event is sufficiently discomforting so as to limit or interfere with daily activities; may require interventional treatment [eg, fever requiring antipyretic medication]).
- Grade 3 = Severe (event results in significant symptoms that prevent normal daily activities; may require hospitalization or invasive intervention).
- Grade 4 = Life threatening or disabling.
- Grade 5 = Death.

AEs will be reported with an individual start and stop date for each level of severity.

7.4 Causality Relationship of AEs

The relationship of each AE to each study drug (bempegaldesleukin or placebo) as applicable will be evaluated by the Investigator using the following definitions:

- Not related: An AE that does not follow a reasonable temporal sequence from administration of study drug(s), and/or that can be reasonably explained by other factors such as the patient's medical history, preexisting medical condition, underlying disease, concurrent illness, or concomitant medications/therapies.
- Related: There is a reasonable possibility that the AE is caused by the study drug(s). A plausible temporal sequence exists between the time of administration of the study drug(s) and the development of the AE, or follows a known pattern to the study drug(s). The AE cannot be reasonably explained by the known characteristics of the patient's clinical state or other concomitant therapies or interventions administered to the patient.

7.5 AE Reporting and Follow-up

After initiation of study drug treatment, all AEs will be reported from the time of first study drug(s) administration until 30 days of last dose of study drug(s). For SAEs, additional reporting requirements also apply (see Section 7.7).

All ongoing AEs will be followed until resolution, the patient is lost to follow-up, patient death, or until the Safety Follow-Up call, whichever is earlier. In case the AE has not completely resolved by the Safety Follow-Up call, the final outcome of these ongoing AEs that are not related to study drug will be captured as "Not Recovered/Not Resolved" or "Recovering/Resolving", whichever is applicable. Any ongoing AEs at the Safety Follow-up call that are considered related to study drug will be followed until the event is resolved (with or without sequelae) or deemed stable. Any new AEs occurring after the Safety Follow-Up call will not be captured unless related to a study drug.

For specific instructions on identifying and reporting SAEs, see Sections 7.6 and 7.7.

7.6 Serious AE Definition

An SAE is defined as any untoward medical occurrence that at any dose:

- Results in death.
- Is life threatening, ie, in the opinion of the Investigator, the AE places the patient at immediate risk of death from the event as it occurred; it does not include a reaction that, had it occurred in a more severe form, might have caused death.
- Requires inpatient hospitalization or prolongation of an existing hospitalization that occurs during the course of a patient's participation in a clinical study.
- Results in persistent or significant disability or incapacity.
- Is a congenital anomaly or birth defect.
- Is an important medical event that, based upon appropriate medical judgment, may jeopardize the patient and may require medical or surgical intervention to prevent one of the other outcomes listed above.

Death is an outcome of an AE and not an AE in itself. All events leading to death, regardless of causality, must be reported. An efficacy failure is not considered an SAE. "Life-threatening" means that the patient was at immediate risk of death from the event as it occurred. This does not include an event that might have led to death if it had occurred with greater severity. "Inpatient hospitalization" means the patient has been admitted to a hospital for medical reasons for any length of time. The Investigator should attempt to establish a diagnosis of the event based on signs, symptoms, and/or other clinical information. In such cases, the diagnosis will be documented as the AE and/or SAE and not the individual signs/symptoms.

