5.3.2.1.1 DLTs Related to Study Drug

AEs related to study drug(s) that will be defined as a DLT include the following:

- Any Grade \geq 3 drug-related AE.
- Any Grade ≥ 3 drug-related laboratory abnormality that is clinically significant per the Investigator.
- Respiratory compromise or other virus-related AE attributed to worsening COVID-19, such as severe hypoxia, cyanosis, or chest pain/pressure.

All AEs that meet DLT criteria must be recorded in the electronic data capture system within approximately 24 hours of awareness.

Each AE reported as related to study drug that meet any of the above definitions will be adjudicated by the CRC. If the event is confirmed to be at least possibly related to study drug, meets any of the above definitions, and is confirmed to have occurred in a patient treated with bempegaldesleukin, the event will be considered to be a DLT.

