5.4 Study Stopping Criteria

The study will be promptly paused if any of the following are met:

- Death in any patient in which the cause of death is judged to be related to the study drug by the treating Investigator.
- The occurrence in any patient of a life-threatening SAE whose causal relationship to study drug is judged to be related by the treating Investigator.
- If at any dose tested, there are 2 occurrences of treatment-related dose-limiting toxicities defined in Section 5.3.2.1.1 observed in the first 5 or fewer patients dosed with bempegaldesleukin that are adjudicated by the CRC as meeting the criteria of Section 5.3.2.1.1 and are confirmed as related to study drug in patients actually treated with bempegaldesleukin.

If any of the above listed event(s) occur, patient accrual will be suspended pending further review by the CRC and prompt consultation with the US FDA and Institutional Review Boards (IRBs)/ Independent Ethics Committees (IECs).

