7.7 Serious AE Reporting

Serious AEs occurring after the patient has provided informed consent, but before the first dose of study treatment, will be collected as medical history unless the event is either new and attributed to protocol-mandated procedures by the Investigator or there is a significant change in the rate of occurrence or an increase in the severity of the pre-existing condition which is judged to be clinically important and attributed to the protocol-mandated procedures by the Investigator. Any new or clinically significant changes in the patient's medical that occur after the first dose of drug and meet the SAE criteria will be recorded as SAEs.

All SAEs, regardless of causality, with an onset within 30 days after the last dose of study drug(s) will be reported to Nektar Therapeutics Drug Safety immediately without undue delay, under no circumstances later than 24 hours following knowledge of the event.

In addition, SAEs that are assessed by the Investigator as related to study drug(s) and occurring after the SAE reporting period will also be reported to Nektar Therapeutics Drug Safety immediately without undue delay, under no circumstances later than 24 hours following knowledge of the event.

SAEs must be reported to Nektar Therapeutics Drug Safety via email or Fax as listed at the beginning of this protocol. Nektar Therapeutics may transition to reporting of SAEs via EDC while the study is ongoing. If this occurs, all sites will receive documented instructions regarding how to enter SAEs into EDC. If the study were to transition to reporting of SAEs in EDC, sites would continue to submit SAEs via email or Safety Fax as a backup system should there be EDC system access issues.

The Investigator must complete the SAE Report Form, assess the causality relationship to the study treatment as applicable, and send the completed SAE form via email or fax to Nektar Therapeutics Drug Safety. A follow-up report and any additional records (such as hospital records, consultant reports, and autopsy findings) will be emailed or faxed to Nektar Therapeutics Drug Safety immediately without undue delay, under no circumstances later than 24 hours following knowledge of the follow-up information. Any medication or other therapeutic measures used to treat the event will be recorded.

All SAEs will be followed as described in Section 7.8.

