7.6 Efficacy Analyses

7.6.1 Analysis of Percentage of Patients Who Require Supplemental Oxygen

Number and percentage of patients who require supplemental oxygen will be provided by treatment group and total for Treated Population.

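### The SAE definition exempts an undefined efficacy failure, so non-fatal serious COVID-19 worsening judged unrelated may go uncounted and unreported as an SAE

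*Protocol*

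**What the plan says.** Protocol 7.6 opens broadly: "An SAE is defined as any untoward medical occurrence that at any dose" meets one of the listed seriousness criteria. The paragraph after the list adds two sentences that matter here: "All events leading to death, regardless of causality, must be reported", and "An efficacy failure is not considered an SAE". The second has no qualifier. Neither document says what an efficacy failure is.

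The SAP has a section headed Efficacy Analyses (7.6). It covers:
- oxygen need: "Number and percentage of patients who require supplemental oxygen will be provided by treatment group and total for Treated Population";
- shift on the WHO Clinical Progression Scale, in either direction (7.6.2), and status on Days 3, 5 and 8 (7.6.3);
- days on supplemental oxygen, non-invasive or high-flow support, mechanical ventilation or ECMO (7.6.4).

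Other sections treat the same clinical event as a safety matter:
- Protocol 7.1, on what counts as an AE: "This definition includes intercurrent illnesses or injuries, and exacerbation of preexisting conditions".
- Protocol 7.7: clinically significant post-dose changes "that occur after the first dose of drug and meet the SAE criteria will be recorded as SAEs". All SAEs with onset within 30 days of dosing go to Drug Safety within 24 hours, whatever their cause.
- Protocol 5.3.2.1.1 lists as a DLT criterion "Respiratory compromise or other virus-related AE attributed to worsening COVID-19, such as severe hypoxia, cyanosis, or chest pain/pressure".
- SAP 11.2 includes the same category among its AE summaries.

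The second limb of the pause rule in Protocol 5.4 is "The occurrence in any patient of a life-threatening SAE whose causal relationship to study drug is judged to be related by the treating Investigator". SAE frequency compared with placebo is a secondary objective (Protocol 3.2).

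**The concern.** The exemption has an effect only if it removes something that would otherwise be an SAE. Of the outcomes that the SAP calls efficacy, clinical worsening of COVID-19 is the one that can meet a seriousness criterion. A site that applies 7.6 literally could therefore record intubation or a prolonged stay as a disease outcome and file no SAE.

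That matters because disease progression and the harm the protocol worries about can look alike. Section 2.1.4.2.7 says that toxicity differences between cancer and COVID-19 patients cannot be excluded. Sections 2.1.4.2.7 and 2.2.4.3 discuss a worsened cytokine milieu and hyperinflammation. Section 2.1.1.1 places natural deterioration about 5 to 8 days after symptom onset, and 5.3.2.1 places likely drug-related AEs 1 to 5 days after dosing. The two clocks start at different points, but the windows can overlap. For a single patient the cause may not be decidable. The comparison with placebo can separate the two, but only if serious events are counted without regard to attributed cause.

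**Working it through.** **Step 1. Which route catches a serious COVID-19 deterioration if a site applies the exemption?**

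| Type of event | Route that does not depend on the SAE label | Left uncovered? |
|---|---|---|
| Fatal | 7.6: reportable whatever the cause | No |
| Diagnosed as CRS | 7.9: SAE process and 24-hour timeline for every CRS event; Appendix 3 grades CRS partly on oxygen and ventilator need | Not for reporting |
| Non-fatal, reported as related, meets DLT criteria | 5.3.2.1.1: EDC entry within about 24 hours and CRC adjudication | Partly: EDC entry is not the SAE report under 7.7 |
| Non-fatal, judged unrelated, not CRS | 7.1 makes it an AE; SAP 11.2 summarises it among AEs | Yes, for the SAE count and the 24-hour report |

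Three apparent safeguards do not close the last row.
- 7.1 secures AE status, not SAE status.
- 7.7 refers to the SAE criteria, which are those of 7.6, exemption included.
- CRC adjudication under 5.3.2.1.1 covers only AEs reported as related. The causality definitions in 7.4 steer an event that the underlying disease can explain towards not related.

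**Step 2. Effect of one reclassified patient.** The planned sizes are 5 active and 5 placebo per cohort (Protocol 9.2) and three cohorts, giving 3 × 5 = 15 per arm if all are filled.
- One dose group: 1/5 = 20%, against 0/5 = 0%, a change of 20 percentage points.
- One pooled arm: 1/15 = 6.7 percentage points. The SAP pools placebo; pooling active patients across doses is done here only for illustration.

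**Step 3. How many such events might occur?** The documents give no rate for this population. Protocol 2.1.1.1 cites, for all reported US cases, 14% hospitalised and 2% admitted to intensive care. As an assumed range over 30 patients:
- at 2%: 30 × 0.02 = 0.6 expected; chance of at least one 1 − 0.98^30 = 45%;
- at 14%: 30 × 0.14 = 4.2 expected; chance of at least one 1 − 0.86^30 = 99%.

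Both are probably high for a selected mild population. Every patient is admitted by design, so the 14% is only a loose proxy for serious worsening.

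**Step 4. The pause rule.** Protocol 5.4 has three limbs: a related death, one related life-threatening SAE, and two adjudicated DLTs in the first five or fewer active patients. Only the second uses SAE status. Let p be the assumed chance per active patient of a related, life-threatening, non-fatal respiratory event. With five active patients:
- second limb available: P(at least 1) = 1 − (1 − p)^5;
- only the two-DLT limb left: P(at least 2) = 1 − (1 − p)^5 − 5p(1 − p)^4.

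| p | At least 1 of 5 | At least 2 of 5 |
|---|---|---|
| 2% | 9.6% | 0.4% |
| 5% | 22.6% | 2.3% |
| 10% | 41.0% | 8.1% |
| 20% | 67.2% | 26.3% |

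The right-hand column applies only if every such event is judged drug-related and also called an efficacy failure. That pairing is unlikely, so the table bounds the loss rather than predicting it.

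The plan contains no calculation of its own on this point to reproduce.

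**The case against.** The strongest reply is that the reading is inferred. No text equates efficacy failure with worsening COVID-19. The protocol, which sites follow, calls these outcomes disease measurement (Sections 8 and 9.6), and the efficacy label comes from the SAP. The term could simply mean lack of benefit, as distinct from an untoward occurrence. This stands as a reason for moderate confidence. It does not remove the problem, because an undefined exemption inside a safety definition leaves the choice to each site.

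A reader might also infer that the exemption disables the pause rule. The documents do not support that. The related-death and two-DLT limbs do not use SAE status, and worsening COVID-19 is a named DLT criterion. The remaining limb needs a related judgement, and an investigator who calls an event efficacy failure is normally attributing it to the disease. An event judged unrelated would not trigger a pause under any label.

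A reader might further infer that only deaths are protected. That overlooks the CRS route in 7.9 and the DLT route in 5.3.2.1.1.

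Finally, the event would stay visible. Blinded safety data are reviewed after each pair of patients, the CRC sees disease measurement data, and the SAP reports oxygen use and WHO status by treatment group. This is correct, and it limits the harm. It supplies neither the SAE count nor the 24-hour report. The SAE summaries are also descriptive, so no formal test depends on them.

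**Conclusion.** The concern holds for a defined group: non-fatal, serious COVID-19 deterioration judged unrelated to study drug and not diagnosed as CRS. For that group a literal reading of 7.6 conflicts with the treatment of worsening as an AE in 7.1 and 5.3.2.1.1. It leaves the SAE count and the report to Drug Safety dependent on how a site reads one sentence. Related events that reach the DLT route are partly exposed, because EDC entry does not replace the SAE report.

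The size is 20 percentage points per event in a five-patient dose group and 6.7 in a pooled arm of 15. These figures show what one reclassified patient does, not how likely reclassification is. In 5.4, one limb of three could be weakened, and only where an event judged related is also labelled efficacy failure.

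The conclusion assumes that sites would take the SAP's use of efficacy as a guide to an undefined protocol term. That is plausible but not stated, so confidence is moderate. The sentence should be changed.

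**What to change.** Delete the efficacy-failure sentence from Protocol 7.6, or replace it with text such as:

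> Worsening of COVID-19 that meets any seriousness criterion in this section is an SAE and is reported under Section 7.7, even though it is also recorded as a disease measurement outcome.

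Add a line to SAP 11.2 that these events appear in the serious TEAE tables, and align the eCRF and SAE completion guidance. The change concerns event classification only; it leaves the pause criteria in 5.4 and all clinical management as written.

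The cost is one protocol sentence, one SAP line and a few more SAE reports for disease progression: about 0.6 to 4.2 over 30 patients under the assumed range in the working, and probably fewer. Progression in the placebo arm would be reported on the same terms, so the comparison is not tilted.
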